Psilocybin-assisted Cognitive Behavioral Therapy for Depression

Study Protocol

Organization's Unique Protocol ID: 21-002134

NCT Number: NCT05227612

June 23, 2023

Study Protocol

Objective: To determine (1) acceptability and initial feasibility of psilocybin as an adjunct to cognitive-behavioral therapy (CBT) for major depressive disorder and (2) determine the effect of psilocybin treatment combined with CBT.

Principal Investigators:

[name]; Assistant Professor of Psychiatry; UCLA Semel Institute ([name]); [contact]. [name] is a licensed clinical psychologist with expertise in the conduct of clinical trials for mood and psychotic disorders. [name] will be responsible for the review and evaluation of information relevant to the safety of the trial. He will also oversee the coordination of the clinical trial, serve as a clinician in the study, manage the study data, and lead the analysis and presentation of the study data.

[name]; Distinguished Professor of Psychiatry; UCLA Semel Institute. [name] is a licensed clinical psychologist and the Director of the UCLA Mood Disorders Program. He has significant expertise in the conduct of clinical trials for mood and psychotic disorders. [name] is the director of the Mood Disorder Clinic at the UCLA Semel Institute in which this study will be conducted. He will have several active roles in this study despite not leading psilocybin or CBT sessions. [name] (along with [name]) will be responsible for the review and evaluation of information relevant to the safety of the trial. [name] has significant expertise in the conduct of clinical trials for mood and psychotic disorders. As such, he will be integrally involved in the supervision and coordination of the psychosocial treatment portion of the study. [name] will provide regular consultation on matters related to the treatment development portion of this study (e.g., assessing feasibility and acceptability of the CBT's integration with the psilocybin sessions). [name] will also help oversee the screening and enrollment of study participants, collection and management of study data, and analysis and presentation of study data.

Sub-Investigators:

[name]; Associate Professor of Psychiatry; UCLA Semel Institute. [name] is a behavioral pharmacologist and the Director of the UCLA Cannabis Research Initiative.

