[name], MPH, MBA; Associate Professor of Psychiatry; UCLA Semel Institute. [name] is a psychiatrist who serves as the Medical Director and lead psychiatrist of UCLA's Behavior Health Access.

[name]; Professor of Psychiatry; Harbor-UCLA Medical Center and UCLA Semel Institute. [name] is a psychiatrist and renowned expert in psychedelic treatment for psychiatric disorders.

Research Facility: UCLA Semel Institute – [name].

Institutional Review Board: UCLA Office of Human Research Protection Program, [name].

Specific Aims

The primary objectives of this clinical investigation are (1) to determine the acceptability and feasibility of joining psilocybin treatment with cognitive-behavioral therapy (CBT) for patients with depression, and (2) to determine the initial effect of psilocybin as an adjunct to CBT for major depressive disorder. Psilocybin will be administered orally in two doses during a 12-session CBT treatment to eligible study participants – a 10mg dose following the third session and a 25mg dose following the sixth session.

We hypothesize that psilocybin as an adjunct to 12 sessions of CBT will

- (1) Be feasible and reviewed favorably by participants,
- (2) Lead to improvements in depressive symptoms.

Background

Psilocybin (3-[2-(dimethylamino)ethyl]-1H-indol-4-yl] dihydrogen phosphate) is a natural product produced by numerous species of *Psilocybe* mushrooms. It is a tryptamine derivative, and in humans is rapidly enzymatically broken down to produce psilocin, which acts as a serotonin agonist (Carhart-Harris et al., 2014; Nichols, 2004). Psilocybin is classified as a Schedule I pharmacological substance by the DEA.

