Cognitive behavioral therapy (CBT) is considered the gold-standard of empirically-based psychosocial treatments for depression (Cuijpers et al., 2013). Thus, CBT may serve as a useful, standardized foundation of psychosocial treatment to provide for patients with depression who are receiving psilocybin treatment. Additionally, psilocybin may help facilitate the uptake of CBT skills. Since psilocybin engenders greater cognitive flexibility and behavioral motivation (e.g., greater openness and social connectedness), it may help facilitate the uptake of CBT skills. Depressed individuals’ negative beliefs and unhelpful behaviors can become quite fixed, which can make treatment progress slow. Together, psilocybin may be a helpful catalyst for the cognitive and behavioral changes that are sought in CBT, and CBT may help to solidify cognitive and behavioral changes that are spurred by the psilocybin experience.

This study seeks to build on the current approaches to psilocybin treatment by combining CBT with the already-established psilocybin + PAT approach to (1) test whether CBT can be feasibly and acceptably added to the current psilocybin treatment modality and (2) to work towards protocolizing the psychosocial treatment that adjoins psilocybin drug therapy.

GENERAL INVESTIGATIONAL PLAN:

This study is a preliminary, proof-of-concept pilot to determine feasibility of the treatment methods and effect sizes. The study design is a single-group, fixed dose trial whereby 30 eligible participants will undergo 12 sessions of CBT during which two doses of psilocybin will be administered— a 10mg dose following the third session and a 25mg dose following the sixth session. Participants will be followed for an additional 3 months following treatment

termination. Study procedures will follow previously established safety guidelines (Johnson et al., 2008).

We hypothesize that psilocybin as an adjunct to 12 sessions of CBT will:

- (1) be feasible and reviewed favorably by participants, with minimal to no adverse effects;
- (2) Lead to reductions in negative thinking, increases in engagement with the environment, and improvements in depressive symptoms over the 7-month study period.

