Participants will be instructed not to drive an automobile or engage in any other potentially dangerous activity for the remainder of the day. The study staff will also orient the identified support person to whom the participant is being released to be available to provide emotional support, if necessary, but also to provide space if the participant would rather be alone. Each participant will be given one of the study clinician's direct pager/cellphone number to call if he/she needs support prior to their next CBT session. Within a couple of days following the drug session, participants will conduct their next weekly session of CBT, where the study clinician will inquire about any persisting or adverse effects of the psilocybin.

PARTICIPANTS:

Participants will be adults (ages 21-60) who meet current criteria for major depressive disorder.

STUDY INCLUSION AND EXCLUSION CRITERIA:

All participants must meet the following inclusion criteria to be eligible for the study:

- Ages 21-60,
- Able to swallow capsules,
- Patients with a current major depressive episode or a history of major depressive episodes based on the DSM-5 criteria (American Psychiatric Association, 2013),
- Active current depressive symptoms (i.e., scores >16 on the Hamilton-Depression Rating Scale covering the prior 2 weeks; Hamilton, 1986),
- Have an identified support person who can pick up the individual from UCLA Semel Institute and drive individual home following psilocybin sessions,
- For women of child-bearing potential – using one form of highly effective contraception (e.g., oral contraceptive pill) and willingness to continue contraceptive use for duration of study. Must be willing to take on-site pregnancy tests.
- Agree to refrain from any psychoactive drug (including alcohol) within 24 hours of each drug session and during the drug sessions. Participants will be allowed to consume their usual amount of caffeine prior to and after the drug sessions.
- Agree to not take any PRN medications on the mornings of the drug sessions
- Patient has been medically cleared for the study by a physician
- Participants must remain on anti-hypertensive medications if prescribed previously to manage hypertension

Participants will not be enrolled in the study if they meet any of the following exclusion criteria:

- A personal or family history (first or second-degree) of psychosis or bipolar disorder

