PRIMARY OUTCOME MEASURES AND STATISTICAL ANALYSIS PLAN:

The study's primary assessments will be held prior to starting the CBT (i.e., baseline), within two weeks following the CBT's completion, and three months following the treatment's completion. Secondary measurements will also be collected immediately following each drug session. The study will terminate following the three-month follow-up assessment. A schematic of the study design is presented in Figure 1 below.

To determine feasibility, we will track the number of participants engaged at each phase of screening (i.e., phone screen, physical screen, and psychological screen), the number consented and enrolled, and the number who completed the 4-month treatment. Acceptability was measured by participants at the post-treatment assessment using the Client Satisfaction Questionnaire 8 (CSQ-8; Larsen et al., 1979). Participants' and clinicians' quantitative and qualitative feedback will be collected, using an internally-created questionnaire containing 5-point scales of helpfulness. Depressive symptom severity over the previous 1-2 weeks will be assessed using the 17-item Hamilton Depression Rating Scale (HAM-D; Hamilton, 1986). Psychosocial functioning over the two weeks prior to the assessment will be rated by a study assessor assessed using the 100-point Global Assessment of Functioning Scale (GAF; American Psychiatric Association, 2000).

Feasibility metrics will be tabulated by calculating percentages of participants enrolled and retained through the treatment divided by the total number of participants consented and screened. Acceptability metrics will be calculated based on the participant-rated CSQ-8. We will calculate the mean and standard deviation. We will examine within-subjects changes in depressive symptoms (HAM-D) and functioning (GAF) using repeated measures analyses of variance (ANOVA) in IBM's SPSS version 30.0. Time will be the independent fixed factor variable, based on the interval assessments of the study (baseline, post-treatment, follow-up).

Figure 1. Study Design Schematic for Eligible Participants

STUDY DRUGS:

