We will thoroughly assess for psychiatric contraindications by gathering personal and family psychiatric history of psychotic, bipolar, and personality disorders. Additionally, any participants whose psychiatric symptoms require acute treatment (e.g., severe suicidal ideation) will be excluded. Suicidal ideation and behavior will be assessed via clinician-based assessment on the Hamilton-Depression Inventory and the Columbia Suicide Severity Rating Scale at each study assessment as well as the Depressive Disorders Module of the Structured Clinical Interview for DSM-5 Disorders at the baseline screening assessment. Additionally, participants will self-report on suicidal ideation on the Patient Health Questionnaire and Quick Inventory of Depressive Symptomatology at each study assessment.

Following a thorough screening of participants' physical and psychiatric status, further safety precautions will be in place throughout the course of the study. Prior to the first drug administration, each participant will undergo approximately 3-4 hours of preparation for the drug. These preparatory sessions will overlap with the beginning of the psychosocial treatment (CBT). In these sessions, the therapist will begin to develop rapport with the participant, discuss meaningful aspects of the participant's life, and discuss the range of experiences to be expected from the drug. The therapist and the patient will also discuss the patient's intentions for the drug session, which will include seeking a better understanding of the causes and consequences of their mood difficulties as well as exploring ways to improve their depression.

Additionally, participants will be prepared with strategies to overcome difficult experiences during the drug session. Relative to other classes of drugs, the subjective effects of psilocybin are more variable and more difficult to describe. Therefore, sufficient time to fully discuss the potential effects of the drug, provide recommendations for how to respond to various experiences, and to answer the participants' questions and concerns will help ensure that the

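### Objective 2 as worded in Specific Aims, the effect of psilocybin as an adjunct to CBT, is not identified by a single-group design analysed on time alone

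*Combined protocol and SAP*

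**What the plan says.** The second objective is worded in two ways. The opening Objective statement says "determine the effect of psilocybin treatment combined with CBT". Specific Aims, which lists it as a primary objective, says "to determine the initial effect of psilocybin as an adjunct to CBT for major depressive disorder". The hypotheses in Specific Aims and in the General Investigational Plan also speak of psilocybin as an adjunct to 12 sessions of CBT.

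The General Investigational Plan states: "The study design is a single-group, fixed dose trial whereby 30 eligible participants will undergo 12 sessions of CBT", with two psilocybin doses during that course. It adds: "This study is a preliminary, proof-of-concept pilot to determine feasibility of the treatment methods and effect sizes".

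Under Primary Outcome Measures and Statistical Analysis Plan, the study's "primary assessments will be held prior to starting the CBT (i.e., baseline"), then within two weeks of the end of CBT, then three months after treatment. HAM-D and GAF go into a repeated measures ANOVA whose one factor is time, at those three levels. Secondary measurements follow each drug session, but their instruments are not named and they do not appear in the analysis. The part on participant worsening or non-response says symptoms are monitored at visits, again without an instrument or an analysis.

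Entry requires "scores >16 on the Hamilton-Depression Rating Scale covering the prior 2 weeks". The Potential Benefits section credits both psilocybin and CBT with antidepressant effects in major depressive disorder.

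**The concern.** An adjunct effect is an increment: the outcome under CBT with psilocybin, less the outcome under CBT without it. Estimating it needs some planned observation in which CBT is present and psilocybin is not. The analysed data have none.

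The change from baseline therefore combines psilocybin, CBT, the natural course of depression (which the protocol itself recognises among its risks), expectancy in an open treatment, and regression to the mean after entry on a high HAM-D score. The study is meant to supply effect sizes. If the pre-post effect size is carried forward under the Specific Aims wording, a later trial could be planned around a psilocybin increment that was never measured.

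**Working it through.** **The plan's own figure.** The only design number is N = 30. No alpha, power, effect size, SD or dropout rate is given, so it cannot be reproduced. The point does not depend on it.

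**Step 1: identifiability.** Code what has been delivered by each analysed HAM-D visit, under the planned treatment.

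| Visit | CBT (C) | Psilocybin (P) |
|---|---|---|
| Baseline, before CBT | 0 | 0 |
| Within 2 weeks after CBT | 1 | 1 |
| 3 months after treatment | 1 | 1 |

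Write the expected score as a + b·C + c·P. Since C = P at every visit, this equals a + (b + c)·C. The design matrix (intercept, C, P) has rank 2 of 3, so only b + c is estimable. That sum is also inseparable from time, because C switches on exactly when baseline ends. Adding participants repeats the same three rows. A concurrent CBT-only group would add rows with C = 1 and P = 0 and bring the rank to 3 of 3.

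**Step 2: distance from the doses.** The Safety Measures section says monitoring to the end of the study reaches 6 months after the first dose and 5 months after the second. The last assessment is 3 months after treatment. The doses therefore fall about 6 − 3 = 3 and 5 − 3 = 2 months before treatment ends. The first analysed post-baseline HAM-D comes after that interval, with further CBT in between.

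**Step 3: what a significant time effect would show.** Assume a two-sided 0.05 test, no psilocybin increment, and a CBT-plus-time change of d (mean change divided by SD of change). For the baseline to post-treatment comparison, power is the probability that a noncentral t with n − 1 degrees of freedom and noncentrality d√n exceeds the 97.5% t quantile. At n = 30 and d = 0.5 the noncentrality is 0.5 × √30 = 2.74.

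| d | n = 30 | n = 20 completers |
|---|---|---|
| 0.3 | 36% | 25% |
| 0.5 | 75% | 56% |
| 0.8 | 99% | 92% |
| 1.0 | >99% | 99% |

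The values of d and the 20 completers are assumptions.

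**Step 4: what the design can deliver.** For change under the combination, the 95% CI half-width is t(0.975, 29)/√30 = 0.37 SD of the change, or 0.47 SD with 20 completers. At n = 30, 80% power is reached at d = 0.53.

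**Step 5: regression to the mean, illustration only.** The expected fall is (1 − reliability) × SD × φ(z)/(1 − Φ(z)), with z = (16.5 − mean)/SD. The documents give no mean, SD or reliability. I assumed a screened mean of 14 to 20, SD 5 to 6 and reliability 0.6 to 0.8.

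- Low end (mean 20, SD 5, reliability 0.8): z = −0.70, ratio 0.412, so 0.2 × 5 × 0.412 = 0.41 points.
- High end (mean 14, SD 6, reliability 0.6): z = 0.417, ratio 1.081, so 0.4 × 6 × 1.081 = 2.59 points.

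This also assumes that the screening HAM-D serves as the baseline. The screening section places a HAM-D rating there and no separate later baseline is described, but the analysis section says only that baseline precedes CBT.

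**The case against.** The best defence is that this is a self-described proof-of-concept pilot, for which one arm is an ordinary choice. The opening Objective statement already names the combination. The Background asks whether CBT can be added to psilocybin treatment, not what psilocybin adds to CBT. The hypothesised result is improvement under the combination, and the analysis section promises only within-subject change. All of that stands. It narrows the fault to the adjunct wording in Specific Aims and the hypotheses. It does not remove it, because that wording defines a primary objective.

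A reader might infer four stronger things that the documents do not support.

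- *That the sponsor will report a time effect as psilocybin's effect.* No passage says so. The analysis is described neutrally and names no contrasts.
- *That depression is never assessed between baseline and the end of treatment.* Unnamed measurements follow each drug session, symptoms are monitored at visits, and the design schematic (Figure 1) was not visible in the text I worked from. The safe statement concerns the analysed HAM-D time points. A HAM-D taken on a dosing day would in any case look back 1 to 2 weeks, mostly to before that dose.
- *That session-level ratings would isolate psilocybin.* Each dose would stay confounded with ongoing CBT, time and expectancy. Sessions 1 to 3 are preparatory, with CBT content only as time allows, so the change before the first dose is not a CBT-only trend to project forward.
- *That participants kept in CBT after psilocybin is stopped form a comparator.* The protocol does retain them, but they are selected by adverse reaction, worsening or a newly started restricted drug, and no analysis uses them.

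**Conclusion.** The point holds as one of identification. Objective 2 as worded in Specific Aims cannot be answered at any N, because planned CBT and psilocybin exposure coincide at every analysed HAM-D visit. That conclusion needs no outside figure. The opening Objective statement and Specific Aims also state different estimands for the same objective.

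The significance probabilities rest on an assumed two-sided 0.05 and assumed changes. The 0.4 to 2.6 HAM-D points for regression to the mean rest wholly on assumed inputs and on the inference that the screening score is the baseline. They should not be read as an estimate for this trial.

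The feasibility and acceptability aims are unaffected, and the design can estimate change under the combined treatment. Neither the sample size nor the choice of a single arm for a pilot is being called wrong. The correction should be made because it governs what the trial may conclude.

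**What to change.** 1. **Reword (the necessary change).** In Specific Aims, restate objective 2 as: *estimate the uncontrolled within-person change in HAM-D under combined psilocybin and CBT, with 95% CI*. Align the adjunct hypotheses in Specific Aims and the General Investigational Plan. In the analysis section, state that the change and its effect size will not be attributed to psilocybin. The opening Objective statement is already close to this. The cost is wording and a more modest claim; N does not change.

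2. **Optional, descriptive only.** The protocol already has depression self-report scales: "participants will self-report on suicidal ideation on the Patient Health Questionnaire and Quick Inventory of Depressive Symptomatology at each study assessment". Give one of them at existing CBT sessions, including the last before each drug session, and report change from the score before the first dose beside change from baseline on that scale. This shows when change occurs and takes early change and some regression to the mean out of the later figure. It does not isolate psilocybin. The cost is a few minutes per session.

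3. **Before any phases are defined**, reconcile the passages on the second drug session. Specific Aims and the dosing paragraphs of the General Investigational Plan place it after session 6; the session-by-session outline places it after session 7.

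A concurrent CBT-only arm would identify the increment but is not requested here. Splitting 30 as 15 v 15 detects about (1.960 + 0.842) × √(2/15) = 1.02 SD with 80% power and has 28% power for 0.5 SD, which would need 63 per arm (two-sided 0.05, assumed effects).

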If participants must take a nonprescription medication, participants will be asked to stop using it for 24 hours before a psilocybin session. Pain relievers containing only aspirin, ibuprofen, or acetaminophen are acceptable for normal use without special permission. Participants must also agree to leave urine samples upon request or to take a breathalyzer test to allow the study team to monitor participants' compliance with the drug and alcohol restrictions.

-Cognitive behavioral therapy (CBT)

There are no significant risks of CBT; however, CBT does involve asking patients to engage in activities that can be aversive and/or opposite of their typical thoughts and behaviors. As such, participants may experience discomfort as a result to engaging in CBT skills such as cognitive restructuring, behavioral activation, relaxation exercises.

-Depressive symptoms

Cognitive-behavioral therapy and psilocybin have been shown to have a beneficial effect of depressive symptoms. Nonetheless, it is possible that depressive symptoms will worsen during the study. An increase in depressive symptoms could be due to the study interventions (including psilocybin), not continuing in standard clinical care, or the natural course of depression. Depressive symptoms which could worsen include, but are not limited to: suicidal thoughts, low mood, feeling hopeless or guilty, fatigue, lack of pleasure, poor concentration, and change in sleep or appetite.

-Alcohol restrictions

The effects of psilocybin may interact with alcohol. This means that if participants consume alcohol while the drug is in their system, they could experience magnified or unpredictable effects of the drug, which could impair their ability to do everyday tasks such as driving an automobile. Such undesirable effects are possible for at least 24 hours following a visit to the research unit. Therefore, participants will be asked to not consume alcohol for a period of at least 24 hours before and 24 hours following the psilocybin session.

-Activity restrictions

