For safety reasons, participants will not be allowed to drive themselves home after a day-long psilocybin session. It is possible that effects of psilocybin may persist after the time participants are scheduled to leave the research unit. We recommend participants stay with a trusted friend or relative overnight and that they refrain from operating dangerous machinery or a motor vehicle for at least 24 hours after psilocybin administration. Participants may also be asked by the study team to restrict other activities or to stay at the research unit until psilocybin effects lessen.

-Psychological risks

Some of the questions the therapist and researchers ask participants may be upsetting, or participants may feel uncomfortable answering them. Participants may get tired or bored when we are asking questions or are completing questionnaires. If participants do not wish to answer a question, you can skip it and go to the next question.

-Confidentiality

Although we will do our best to keep your participation in this study confidential, taking part in this study may entail the unlikely risk of loss of confidentiality of sensitive information.

-Unknown risks

There may be side effects and discomforts of this study that are not yet known.

2. ADEQUACY OF PROTECTION AGAINST RISKS:

Recruitment and Informed Consent:

Flyers will be available at appropriate locations (e.g., approved UCLA bulletin boards and UCLA Semel outpatient clinic waiting rooms). Information about the study will be sent to relevant groups and may be posted on their group social media pages. Examples of these include the Bipolar and Depression Support Alliance (DBSA) and local chapters of the National Alliance on Mental Illness (NAMI). Study flyers will also be sent to local mental health providers and local school counselors and mental health personnel.

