For the psilocybin sessions, participants must agree to remain at the UCLA Semel Institute until the research team says they are ready to leave. At the end of the sessions, they must be driven home by a trusted support person who has been identified to the study staff. The study staff will release the participant to this identified person at the end of the psilocybin session. However, if the UCLA staff believes it is necessary for safety reasons, the participant will stay overnight. If the participant stays overnight, the UCLA staff will interview the participant before they return home.

Exclusion criteria:

The following exclusionary criteria are designed to minimize the risks to participants:

- Currently receiving cognitive behavioral therapy,
- A personal or family history (first or second-degree) of psychosis or bipolar disorder
- Resting blood pressure above 140 systolic, 90 diastolic or heart rate > 90 beats per minute (averaged across four separate measurements)
- Meeting criteria for a DSM-5 cluster B personality disorder (narcissistic, histrionic, borderline, antisocial personality disorder),
- Active suicidality (i.e., HAM-D item 3 score of 3 or greater) or other psychiatric disturbance requiring acute treatment

- Current use of antidepressants or other serotonergic-affecting substances (e.g., St. John's Wort and 5-hydroxytryptophan), lithium, or efavirenz [regardless of whether the drug(s) is/are prescribed for MDD or other conditions]
- Current use of opioids (e.g., codeine, fentanyl, hydrocodone, meperidine, tramadol)
- Any of the following cardiovascular conditions: uncontrolled hypertension, coronary artery disease, congenital long QT syndrome, cardiac hypertrophy, cardiac ischemia, congestive heart failure, myocardial infarction, tachycardia, artificial heart valve, a clinically significant screening ECG abnormality, or any other significant cardiovascular condition
- QTc interval measurement of > 450 ms in males or > 460 ms in females as measured by the baseline ECG
- A history of stroke or Transient Ischemic Attack (TIA)
- Epilepsy or history of seizures
- Insulin-dependent diabetes
- Meeting criteria for a DSM-5 substance abuse or dependence within prior 6 months (including for nicotine and cannabis)
- Positive urine drug screen for illicit substances (excluding cannabis)
- Use of other psychedelics or ketamine within prior 12 months
- Adverse prior reaction to a psychedelic agent
- Pregnant, trying to get pregnant, or nursing

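### The driving restriction given at release ends with the day, short of the 24 hours that the protocol recommends for driving and dangerous machinery

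*Combined protocol and SAP*

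**What the plan says.** Two places in the protocol tell participants how long to stay off the road after they have left the site.

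- **General Investigational Plan, release after a drug session.** "Participants will be instructed not to drive an automobile or engage in any other potentially dangerous activity for the remainder of the day". This is what staff are to tell the participant at release. It gives no hour count and does not define when the day ends.
- **Potential Risks, Activity restrictions.** Participants are advised to spend the night with someone they trust and to "refrain from operating dangerous machinery or a motor vehicle for at least 24 hours after psilocybin administration". The text introduces this advice with a reason: "It is possible that effects of psilocybin may persist after the time participants are scheduled to leave the research unit". The same paragraph gives the team further discretion: "Participants may also be asked by the study team to restrict other activities or to stay at the research unit until psilocybin effects lessen".

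The journey home is covered separately and consistently. Activity restrictions bars self-driving after the session, and the Set and Setting text says "they must be driven home by a trusted support person". That text also allows for a night on site: "However, if the UCLA staff believes it is necessary for safety reasons, the participant will stay overnight".

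No passage reconciles the two periods.

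**The concern.** The shorter period sits in the operational procedure as an instruction. The longer one sits in the risk section as a recommendation. A clinician who discharges a participant by following the release paragraph would state the shorter limit. The participant could then obey that instruction to the letter and still drive inside the window in which the protocol advises against it.

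What is at stake is participant safety in a narrow case: someone whose drug effects seem to have resolved at release, but persist or return, and who drives overnight or early the next morning. No endpoint, estimate, sample size or analysis depends on this.

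**Working it through.** The plan states no figure to reproduce. The check sets the two statements side by side and then does clock arithmetic.

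**Side by side**

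| | Release paragraph | Activity restrictions |
|---|---|---|
| Force | Instruction | Recommendation |
| Scope | Driving and any other potentially dangerous activity | Dangerous machinery and motor vehicles |
| End point | End of the day, undefined | At least 24 h from dosing |

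The scopes overlap on driving. Dangerous machinery is named only in the second, though it would naturally count as a dangerous activity under the first. For other dangerous activity the protocol gives no 24-hour period, so there is no shortfall there to measure.

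**Inputs**

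- Dosing time 9:00: the ideal time on the 10 mg case report form (Appendix I). The 25 mg session is assumed to be the same.
- Recommended period: 24 h from dosing (Activity restrictions).
- End of the day: not defined. Midnight is assumed, with 22:00 and 07:00 the next morning as alternatives.
- Usual duration of drug effects: 5 to 7 h (Potential Risks).
- Number of releases: 30 participants and two drug sessions each (General Investigational Plan), so at most 30 x 2 = 60.

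**Formula.** Uncovered time = 24 h - (end of day - dosing time).

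| Dosing | End of day | Instruction covers | Uncovered |
|---|---|---|---|
| 9:00 | midnight | 15 h | 24 - 15 = 9 h |
| 8:30 (assumed) | midnight | 15.5 h | 24 - 15.5 = 8.5 h |
| 10:00 (assumed) | midnight | 14 h | 24 - 14 = 10 h |
| 9:00 | 22:00 | 13 h | 24 - 13 = 11 h |
| 9:00 | 07:00 next day | 22 h | 24 - 22 = 2 h |

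The gap is above zero in every row. It does not depend on discharge time or session length, because one limit is tied to the calendar day and the other to dosing.

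**Against the usual duration of effects.** With 9:00 dosing and a midnight end, the instruction still runs 15 - 7 = 8 h to 15 - 5 = 10 h beyond the usual end of effects. The uncovered hours therefore fall well after most participants would be expected to have recovered, and they lie mostly overnight.

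**The case against.** The strongest reply is that there is no inconsistency: a firm same-day instruction backed by longer advice is a coherent two-tier rule. It is true that the statements are compatible. A reader might infer that the protocol contradicts itself, and it does not. What remains is that the tier staff are told to deliver at release is the shorter one.

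Second, the 24-hour advice may well reach participants anyway. Participant Education says that the risks are conveyed through the consent form and in discussion. The consent pages are not in the public text, so their wording cannot be checked, and nothing says that the release sentence is the only advice given. A reader might infer that participants are never told 24 hours; the documents do not show that.

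Third, existing safeguards are substantial. Release requires that effects have resolved, at least 6 hours after dosing, with the participant fully oriented, not in acute distress, and with normal blood pressure and heart rate. The sentence on persisting effects refers to the scheduled leaving time, and the same paragraph lets the team keep the participant on site. A night with a trusted person is recommended, and each participant has a clinician's direct number. All this stands and makes the residual risk small. None of it sets how long the participant should stay off the road.

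Fourth, the Alcohol restrictions text might be read as independent support, since it describes effects "which could impair their ability to do everyday tasks such as driving an automobile" and adds: "Such undesirable effects are possible for at least 24 hours following a visit to the research unit". It is not support. Those statements concern drinking while the drug is in the body, and alcohol already has its own 24-hour restriction.

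Finally, it is tempting to say that every dangerous activity should be barred for 24 hours. The protocol's 24-hour advice covers machinery and motor vehicles only, so that would be a new requirement.

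**Conclusion.** The point holds in a limited form. On driving, the release instruction is shorter than the protocol's own recommended period, by about 9 hours for a 9:00 dose if the day ends at midnight, and by 2 to 11 hours on the other readings tried. These figures rest on the assumed end of the day and on the 10 mg form's dosing time holding for both sessions. The instruction is given at up to 60 releases.

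The hours measure time without an instruction. They say nothing about how often harm would follow: the documents give no rate of effects persisting or returning after release, so the risk cannot be sized. Given the release criteria, it is likely to be small. This is a cheap improvement to the wording of a safety procedure and has no bearing on the statistical plan.

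**What to change.** Replace the release sentence in the General Investigational Plan with wording to this effect: *At release, staff will tell participants not to drive or use dangerous machinery until at least 24 hours have passed since dosing, and to avoid other potentially hazardous activities until the end of that day.* This brings the instruction into line with the existing recommendation and adds no new period for other activities.

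Two optional additions follow. Staff could mention the 24-hour driving limit in the orientation they already give the support person. If the consent form states the shorter period, it should be matched.

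The cost is one sentence, possibly one spoken point, and a consent edit if needed. For participants, the instructed restriction on driving and machinery lengthens by about 9 hours after each of two sessions on the main assumptions, so some may need a lift early the next morning.
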